6.5.1.4. Prior Anti-cancer Therapies

The prior anti-cancer therapies are collected under the eCRF page related to prior non-drug locoregional treatment and ‘Prior Cancer Therapy’, ‘Prior Radiation Therapy’ and ‘Prior Surgery’ eCRF pages.

The prior anti-cancer locoregional therapies are collected under the eCRF page related to prior non-drug locoregional treatment and ‘Prior Cancer Therapy’ eCRF pages.

- Locoregional therapies with drug are extracted by verbatim term of ‘Reason for Administration’ in ‘Prior Cancer Therapy’ eCRF pages as below:
 - Transcatheter arterial chemoembolization;
 - Hepatic arterial infusion;
 - Percutaneous ethanol injection;
 - Others (‘Locoregional therapy’ as verbatim term).
- Locoregional therapies without drug are extracted by verbatim term of ‘Treatment’ in the eCRF page related to prior non-drug locoregional treatment as below:
 - Transcatheter arterial embolization;
 - Radiofrequency ablation;

- Cryotherapy;
- Others (verbatim terms other than the above).

The number and percentage of patients in each of the following anti-cancer therapy categories will be tabulated:

- Patients with at least one type of prior anti-cancer treatment;
- Patients with at least one prior anti-cancer locoregional therapy;
- Patients with at least one prior anti-cancer drug therapy other than locoregional therapy (other than locoregional therapy from 'Prior Cancer Therapy' eCRF page);
- Patients with at least one prior anti-cancer radiotherapy;
- Patients with at least one prior anti-cancer surgery.

Prior anti-cancer locoregional therapy with/without drug will be summarized as follows based on the number and percentage of patients with the following:

- At least one prior anti-cancer locoregional therapy;
- Number of times of prior transcatheter arterial chemoembolization (TACE): missing, 0, 1, 2, 3, ≥ 4 ;
- Locoregional therapy: Transcatheter arterial embolization (TAE), TACE, Hepatic arterial infusion (HAI), Percutaneous ethanol injection (PEI), Radiofrequency ablation (RFA), Cryotherapy, Others.

Prior anti-cancer drug therapy will be summarized as follows based on the number and percentage of patients with the following:

- At least one prior anti-cancer drug therapy;
- Number of prior anti-cancer drug therapy regimens: missing, 0, 1, 2, 3, ≥ 4 ;
- Intent of Drug Therapy: Neo-Adjuvant, Adjuvant, Advanced-Metastatic, Locoregional Disease-Recurrence;
- Best response: CR, PR, SD, PD, Unknown, Not applicable. Best response is derived from the last treatment regimen.

The drugs for prior anti-cancer locoregional therapies and prior anti-cancer drug therapies will also be summarized based on the number and percentage of patients by the drug class and preferred term, respectively. A patient will be counted only once within a given drug class and within a given drug name, even if he/she received the same medication at different times. The summary will be sorted on decreasing frequency of drug class and decreasing

frequency of drug name in a given drug class. In case of equal frequency regarding drug class (respectively drug name), alphabetical order will be used.

The combined preferred term of drug for prior anti-cancer locoregional therapies, eg, epirubicin/mitomycin, and prior anti-cancer drug therapies will also be summarized based on the number and percentage of patients. A patient will be counted only once within a given clustered drug name, even if he/she received the same medication at different times. The summary will be sorted on decreasing frequency of clustered drug. In case of equal frequency, alphabetical order will be used.

Prior anti-cancer therapies will be included in the listings that follow with a flag to identify prior therapies. These will include the patient identification number, and all the relevant collected data-fields on the corresponding eCRF pages.

- Listing of anti-cancer locoregional therapies with drug, including responses to regimen;
- Listing of anti-cancer locoregional therapies without drug, including responses to regimen;
- Listing of anti-cancer drug therapies, including responses to regimen;
- Listing of anti-cancer radiotherapy;
- Listing of anti-cancer surgeries.

6.5.2. Study Conduct and Patient Disposition

The following analyses will be performed based on the FAS overall and separately by treatment group.

6.5.2.1. Patient Disposition

The percentages below will be calculated based on the number of patients in the FAS.

- Total number of patients screened overall;
- Number of patients who discontinued from the study prior to treatment with study drug overall and by the main reason for discontinuation;
- Number and percentage of treated patients in each of the analysis sets defined in [Section 4](#);
- Number and percentage of patients with study drug ongoing (separately for each study drug when administered in combination);
- Number and percentage of patients who discontinued study drug overall and by the main reason for discontinuation of study drug (separately for each study drug when administered in combination);

- Number and percentage of patients who entered follow-up;
- Number and percentage of patients who discontinued follow-up overall and by the main reason for discontinuation;
- Number and percentage of patients who entered long-term follow-up;
- Number and percentage of patients who discontinued long-term follow-up overall and by the main reason for discontinuation.

In addition the following will be summarized:

- Number and percentage of treated patients by center.

In addition, a cross tabulation of patients who have discontinued/are ongoing treatment with avelumab vs patients who have discontinued/are ongoing treatment with axitinib will also be provided.

6.5.2.2. Protocol Deviations

All protocol violations that impact the safety of the patients and/or the conduct of the study and/or its evaluation will be reported. These include:

- Patients who are dosed on the study despite not satisfying the inclusion criteria;
- Patients who develop withdrawal criteria whilst on the study but are not withdrawn;
- Patients who receive the wrong treatment or an incorrect dose;
- Patients who receive an excluded concomitant medication;
- Deviations from GCP.

The identification of these and other CSR-reportable deviations will be based on the inclusion/exclusion criteria or other criteria presented in the protocol.

6.5.3. Study Treatment Compliance and Exposure

The following analyses will be based on the safety analysis set by treatment group.

Cycle definitions for study drugs that are administered in combination apply to all the study drugs in the combination. Ie, cycle is patient-dependent, rather than study-drug-dependent when study drugs are administered in combination.

For Cycle X, actual cycle start date for each patient is:

- the earliest start date of dosing in the Cycle X Day 1 visit eCRF exposure page, if the patient received study treatment on that visit (ie, any study drug with dose >0 at that visit);

- the first day of assessments in the Cycle X Day 1 visit, if the patient did not receive study treatment on that visit (ie, all study drugs had dose=0 at that visit). Use start date in the exposure page if available; if start date is not available then use date of collection of vital signs on Cycle X Day 1 visit.

Actual cycle end date for each patient is,

- for all cycles X except the last cycle, actual cycle end date = actual cycle (X+1) start date – 1 day;
- for the last cycle, actual cycle end date = actual cycle start date + intended cycle duration (in days) – 1 day.

Cycle duration (weeks) = (actual cycle end date – actual cycle start date + 1)/7

When summarizing exposure for each study drug, only cycles from first dose of study treatment until the last cycle with non-zero dose of at least one of the study drugs should be included.

Exposure may be summarized (per cycle and/or overall) as dose received (cumulative dose, actual dose intensity) and as dose received relative to intended dose (relative dose intensity [RDI]).

The information that will be summarized depends on how the study drug is dosed (eg, infusion cyclical, oral daily, oral cyclical).

The formulae below should be applied to each study drug separately even when study drugs are administered in combination.

The derivations below are provided assuming 1 cycle = 2 weeks and for the following study drugs (administered alone or in combination):

- Avelumab administered as a 1-hour IV infusion at a dose of 10 mg/kg once every 2 weeks in 2-week cycles.
- Axitinib administered orally BID PO at a dose of 5 mg.

6.5.3.1. Exposure to Avelumab

The dose level for avelumab is calculated as actual dose administered/weight (mg/kg). The last available weight of the patient on or prior to the day of dosing will be used.

Intended duration of treatment with avelumab (weeks) =

(end date – date of first dose of study drug + 1)/7,

where end date = start date of last cycle with non-zero dose of study drug + 14 – 1.

Duration of exposure to avelumab (weeks) =

(last dose date of avelumab – first dose date of avelumab + 14)/7.

Cumulative dose in a cycle or overall is the sum of the actual doses of avelumab received in a cycle or overall, respectively.

Actual Dose Intensity (DI)

- By cycle actual DI (*mg/kg/2-week cycle*) = [cumulative dose in the cycle (mg/kg)]/[cycle duration (weeks)/2];
- Overall actual DI (*mg/kg/2-week cycle*) = [overall cumulative dose (mg/kg)] / [intended duration of treatment with avelumab (weeks)/2].

Relative Dose Intensity (RDI)

- Intended DI (*mg/kg/2-week cycle*) = [intended cumulative dose per cycle] / [intended number of 2-weeks in a cycle] = [10 (mg/kg)] / [1 (2-week cycle)] = 10 (mg/kg/2-week cycle)
- By cycle RDI (%) = $100 \times$ [by cycle actual DI] / [intended DI] = $100 \times$ [by cycle actual DI] / [10 (mg/kg/2-week cycle)]
- Overall RDI (%) = $100 \times$ [overall actual DI] / [intended DI] = $100 \times$ [overall actual DI] / [10 (mg/kg/2-week cycle)]

6.5.3.2. Exposure to Axitinib

The dose level is calculated as actual dose administered (mg/day).

Intended duration of treatment with axitinib (weeks) = (end date – date of first dose of axitinib + 1)/7,

where end date = date of last dose of axitinib.

Duration of exposure to axitinib (weeks) =

(last dose date of axitinib – first dose date of axitinib + 1)/7

Cumulative dose is the sum of the actual doses of axitinib received in the study.

Actual Dose Intensity (DI)

- Overall actual DI (*mg/week*) = [overall cumulative dose (mg)] / [intended treatment duration (weeks)]

Relative Dose Intensity (RDI)

- $RDI (\%) = 100 \times [\text{overall cumulative dose}] / [\text{intended cumulative dose per week} \times \text{number of weeks from first dose of study drug to last dose of study drug}]$
 $= 100 \times [\text{overall cumulative dose}] / [7 \times 2 \times 5 \times \text{duration of exposure to axitinib in weeks}]$

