5.4.2. Axitinib

Axitinib will be administered orally BID at approximately the same time in the morning and evening on a continuous dosing schedule, ie, without a break in dosing in the absence of drug-related toxicity (see [Section 5.4.5](#)). Axitinib tablets are to be taken approximately 12 hours apart and may be administered without regard to meals. Tablets must not be crushed, split, or dissolved, and patients should be instructed to swallow the study medication whole without manipulation or chewing of the medication prior to swallowing.

A dosing card will be provided to the patients to provide guidance for the correct use of axitinib.

Patients must be instructed that if they miss a dose or vomit anytime after taking a dose, they must not “make it up” with an extra dose, but instead resume subsequent doses as prescribed. Any missed dose may be taken late, up to 3 hours before the next scheduled dose of that day, otherwise, it should be skipped and dosing resumed with subsequent doses as prescribed. Patient must be instructed to record all doses (missed or vomited doses or extra doses) in a dosing diary supplied by the site. If doses are missed or vomited or if an extra dose is taken, this must be indicated in the source documents and CRFs.

Patients experiencing toxicity may require treatment adjustment or discontinuation according to the guidelines specified in [Table 1](#) and [Table 2](#).

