6.5.3.3. Dose Reductions

Applicable to avelumab. Dose reduction is defined as actual non-zero dose <90% of the planned dose.

Applicable to axitinib. Dose reduction is defined as a change to a non-zero dose level lower than that planned in the protocol.

The number and percentage of patients with at least one dose reduction as well as a breakdown of the number of dose reductions (1, 2, 3, ≥ 4) will be summarized.

For axitinib, patients experiencing dose reduction to 3 mg and to 2 mg are also summarized.

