6.5.3.5. Dose Interruptions

Applicable to axitinib.

An interruption is defined a 0 mg dose administered on one or more days for axitinib. What follows defines how dose interruptions will be counted in the case of multiple dose interruptions.

- If an interruption occurs consecutively for at least two days due to the same reason, then it will be counted only once (example: If the actual dose on Days 1-3 is 10 mg and actual dose on Days 4-5 is 0 mg and dose interruption on Days 4-5 is due to AE, then the total number of dose interruptions is 1).

- If an interruption occurs consecutively for at least two days due to different reasons, then it will be counted for each reason (example: If the actual dose on Days 1-3 is 10 mg and actual dose on Days 4-5 is 0 mg and dose interruption on Day 4 is due to AE and dose interruption on Day 5 is due to dosing error, then the total number of dose interruptions is 2).
- If an interruption occurs for more than one day due to the same reason, but the days are not consecutive, ie, there is at least one dosing day in between, then each dose interruption will be counted as a different occurrence (example: If the actual dose on Days 1, 3 and 5, is 10 mg and actual dose on Days 2 and 4 is 0 mg, and dose interruptions on Day 2 and 4 are both due to dosing error, the total number of dose interruptions is 2).

A dose interruption is not considered a dose reduction.

The number and percentage of patients with dose interruptions and the corresponding reasons will be summarized.

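### The SAP defines axitinib dose level as actual mg per day but tabulates reductions and escalations at per-dose twice-daily levels; applied literally, the mg/day definition counts a half-taken day as a dose reduction

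*SAP*

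**What the plan says.** SAP 6.5.3 gives the planned regimen: "Axitinib administered orally BID PO at a dose of 5 mg". Section 6.5.3.2 then gives the SAP's only definition of axitinib dose level: "The dose level is calculated as actual dose administered (mg/day"). Its formula for relative dose intensity (RDI) uses 7 × 2 × 5 mg per week as the intended dose.

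For axitinib, section 6.5.3.3 states: "Dose reduction is defined as a change to a non-zero dose level lower than that planned in the protocol". It sets no percentage threshold, minimum duration or requirement for a prescribing decision. Avelumab, in the same section, has a 90% threshold. The output is the number and percentage of patients with any reduction, the number of reductions (1, 2, 3, 4 or more), and rows for reductions to 3 mg and to 2 mg. Section 6.5.3.4 treats escalations in the same way, with rows for 7 mg and 10 mg.

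Section 6.5.3.5 covers held doses: "An interruption is defined a 0 mg dose administered on one or more days for axitinib". Its worked example uses daily amounts ("If the actual dose on Days 1-3 is 10 mg and actual dose on Days 4-5 is 0 mg"), and it adds: "A dose interruption is not considered a dose reduction".

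Protocol 5.4.2 requires that partial days be recorded: "If doses are missed or vomited or if an extra dose is taken, this must be indicated in the source documents and CRFs". Protocol Table 1 (section 5.4.5.1) lists the dose levels as 10, 7, 5, 3 and 2 mg BID.

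**The concern.** One term carries two meanings in adjacent sections. A programmer who follows the stated definition works with daily totals. A programmer who follows the named table rows works with per-dose prescribed levels. The two would produce different counts of patients with a reduction or an escalation.

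The mg/day version has a specific weakness. Axitinib is self-administered twice daily, so days with one dose taken and one missed are foreseeable, and so is the half-day when a hold begins after the morning dose. Such a day is not zero, so it is not an interruption, and it is below plan. The count of patients with a reduction would then mix forgotten tablets with prescribed step-downs. That count helps readers judge how well full-dose axitinib is tolerated in the combination, in a trial of about 20 patients where a few misclassified patients move the percentage noticeably.

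**Working it through.** **Planned dose.** From the SAP's RDI denominator, 7 × 2 × 5 = 70 mg per week, and 70 / 7 = 10 mg/day. This agrees with 5 mg BID and with the full-dose days in the 6.5.3.5 example.

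**The two meanings side by side.** The literal mg/day rule is: 0 mg is an interruption, above 0 and below 10 is a reduction, above 10 is an escalation.

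| Situation | mg/day | Literal mg/day rule | Prescribed-level rule |
|---|---|---|---|
| 5 mg BID, both taken | 10 | none | none |
| 5 mg BID, one missed, or hold after the morning dose | 5 | reduction | none |
| 5 mg BID, both missed | 0 | interruption | none (0 mg day) |
| 5 mg BID, one extra dose | 15 | escalation | none |
| 3 mg BID | 6 | reduction | reduction to 3 mg |
| 2 mg BID | 4 | reduction | reduction to 2 mg |
| 7 mg BID | 14 | escalation | escalation to 7 mg |
| 7 mg BID, one missed | 7 | reduction | no further change |
| 10 mg BID | 20 | escalation | escalation to 10 mg |
| 10 mg BID, one missed | 10 | none | no further change |

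Three things follow.

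1. The named rows fail in mg/day. An escalation to 10 mg would be no change from plan, and an escalation to 7 mg would be a fall below it. The rows fit only the Table 1 per-dose levels.
2. Under the written definition a 5 mg day enters the count of patients with a reduction but neither the 3 mg nor the 2 mg row, so the table does not reconcile.
3. Neither a different reference nor a tolerance would cure this. Against the preceding day, 10 to 5 mg is still a fall. A 90% threshold like avelumab's does not help, because 5/10 is 50%.

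**Illustration of size.** Assumptions, none of them in the documents: each dose is missed independently with probability q, no prescribed change occurs, and partial days reach the analysis as daily totals.

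Probability of a half-taken day = 2q(1 − q). Probability of at least one in D days = 1 − (1 − 2q(1 − q))^D. Twelve weeks is D = 84.

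- q = 0.2%: 2 × 0.002 × 0.998 = 0.003992; 1 − 0.996008^84 = 28.5%, or 20 × 0.285 = 5.7 of 20 patients.
- q = 0.5%: 2 × 0.005 × 0.995 = 0.00995; 1 − 0.99005^84 = 56.8%, or 11.4 of 20.
- q = 1%: 2 × 0.01 × 0.99 = 0.0198; 1 − 0.9802^84 = 81.4%, or 16.3 of 20.

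By contrast, one missed 5 mg dose in 12 weeks leaves RDI at (840 − 5) / 840 = 99.4%. RDI handles such days sensibly; a yes/no reduction count does not.

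**The case against.** The strongest reply is that the authors meant the prescribed level. The four named values (3, 2, 7 and 10 mg) are exactly the Table 1 levels around 5 mg BID, and Table 1 uses the term dose level for them. The wording also differs by drug: avelumab's rule compares the actual dose given with plan, whereas axitinib's speaks of moving to another dose level, and a forgotten tablet is not naturally such a move. Protocol 5.4.5 has axitinib dose modifications reported in the CRF, separately from the missed-dose instruction in 5.4.2. The eCRF layout is not shown, so partial days may never reach the exposure data as reduced daily totals.

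Most of this stands. A reader might infer that under this SAP every missed tablet makes the patient a dose-reduction case. The documents do not support that flat statement, because the named rows point the other way. But the SAP never says that prescribed level is meant, and its one definition of the term says something else. The objection therefore identifies the likely intention without removing the conflict.

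Two further inferences also go too far. The sentence separating interruptions from reductions is not contradicted by a partial day before a hold, since it only keeps 0 mg days out of the reduction count. Nor are the adverse events leading to dose reduction distorted: SAP 6.6.1 takes them from the action field on the AE page.

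**Conclusion.** The point holds as an internal inconsistency. The axitinib dose level defined in 6.5.3.2 and the levels tabulated in 6.5.3.3 and 6.5.3.4 cannot both be in force, and applying the written definition gives wrong reduction and escalation counts.

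The existence of the conflict rests on the text alone. Its numerical effect does not. The 29% to 81% range over 12 weeks depends on assumed miss rates, on independence and on how partial days are recorded, and should be read as illustration only.

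A reader might also take this as a flaw in the primary analysis. It is not. The primary endpoints are adverse events and laboratory abnormalities, which SAP 6.1.1.1 refers to sections 6.6.1 to 6.6.5. What is affected is an exposure table that supports the tolerability objective. The correction is worth making before the tables are programmed, but no primary result depends on it.

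**What to change.** In SAP 6.5.3.3 and 6.5.3.4, state that axitinib dose level means the prescribed BID level in protocol Table 1, expressed in mg BID, and count a reduction or escalation only when that prescribed level changes. Report missed, vomited and extra doses separately as compliance. Keep actual mg/day for cumulative dose, dose intensity, RDI and the 0 mg interruptions of 6.5.3.5, and say there that those figures are daily totals.

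The cost is a few lines of SAP text and the matching programming. The protocol already provides for the inputs: the sponsor specifies each patient's dose level in writing before dosing (5.1), axitinib dose modifications are reported in the CRF (5.4.5), and missed doses are recorded there (5.4.2). The eCRF should be checked to confirm that prescribed level and missed doses can be told apart. Treatment and trial conduct do not change.

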6.5.3.3. Dose Reductions

Applicable to avelumab. Dose reduction is defined as actual non-zero dose <90% of the planned dose.

Applicable to axitinib. Dose reduction is defined as a change to a non-zero dose level lower than that planned in the protocol.

The number and percentage of patients with at least one dose reduction as well as a breakdown of the number of dose reductions (1, 2, 3, ≥ 4) will be summarized.

For axitinib, patients experiencing dose reduction to 3 mg and to 2 mg are also summarized.

6.5.3.4. Dose Escalations

Applicable to axitinib.

Dose escalation is defined as a change to a non-zero dose level upper than that planned in the protocol.

The number and percentage of patients with at least one dose escalations as well as a breakdown of the number of dose escalations (1, 2, 3, ≥ 4) will be summarized.

Patients experiencing dose escalations to 7 mg and to 10 mg are also summarized.

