5.1. Allocation to Treatment

All patient will be assigned to starting dose of avelumab 10 mg/kg Q2W plus axitinib 5 mg BID after patients have given their written informed consent and have completed the necessary baseline assessments. The site staff will fax or e-mail a complete Registration Form to the designated sponsor study team member or designee. The sponsor will assign a

patient identification number and supply this number to the site. The patient identification number will be used on all study-related documentation at the site.

No patient shall receive investigational product until the investigator or designee has received the following information in writing from the sponsor:

- Confirmation of the patient's enrollment;
- Specification of the dose level for that patient and;
- Permission to proceed with dosing the patient.

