5.4.5.1. Inpatient Axitinib Dose Escalation and Dose Reduction

Inpatient axitinib dose escalation is permitted up to 10 mg BID and may occur according to the criteria described below.

Patients who tolerate the current axitinib dose without Grade >2 axitinib-related adverse events for 2 consecutive weeks have the option to have their axitinib dose increased (one dose level increase at a time) as indicated in [Table 1](#) (unless the patient's blood pressure [BP] is >150/90 mm Hg or the patient is receiving antihypertensive medication). Particular

attention should be provided to a patient's overall safety profile prior to implementing inpatient axitinib dose escalation.

Table 1. Axitinib Dose Levels

Dose Level	Dose
+2	10 mg BID
+1	7 mg BID
Potential Starting Dose	5 mg BID
-1	3 mg BID
-2	2 mg BID

Patients will be monitored closely for toxicity, and axitinib treatment may be adjusted by dosing interruption with or without dose reduction as indicated in [Table 2](#). Dosing interruption and/or dose reduction by 1, and if needed, 2 dose levels (one dose level decrease at a time) as indicated in [Table 1](#) will be allowed depending on the type and severity of toxicity encountered. Management of patients requiring more than 2 dose reductions of axitinib (one dose level decrease at a time) should be discussed with the sponsor's medical monitor.

Patients who have undergone dose reduction may also undergo dose re-escalation back to the previous dose level at the discretion of the Investigator in the absence of Grade ≥ 2 non-hematologic treatment-related toxicity for at least 28 days.

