	2 systolic BP readings separated by at least 1 hour show systolic pressure >160 mm Hg OR 2 diastolic BP readings separated by at least 1 hour show diastolic pressure >105 mm Hg	
 Withhold until BP is less than 150/100 mm Hg and adjust antihypertensive medication. Then, reduce by 1 dose level and resume treatment. If axitinib dosing is temporarily discontinued, patients receiving antihypertensive medications should monitor closely for hypotension. The plasma half-life of axitinib is 2-4 hours and BP usually decreases within 1-2 days following dosing interruption. See Section 5.4.5.2 for monitoring/management of axitinib-related hypertension. 	
 Continue as per schedule.
	Recurrent hypertension following previous dose reduction (2 systolic BP readings separated by at least 1 hour show systolic pressure >150 mm Hg) OR Recurrent diastolic BP >100 mm Hg (2 BP readings separated by at least 1 hour) following previous dose reduction	
 Repeat dose reduction by one lower dose level. See Section 5.4.5.2 for monitoring/management of axitinib-related hypertension. 	
 Continue as per schedule.

Table 2. Axitinib Dose Modifications and Avelumab Infusion Omissions for Investigational Product-Related Toxicity

Toxicity	NCI CTCAE Severity Grade	Axitinib	Avelumab
		Dose Modification	Treatment Modification
Infusion-related Reaction	Grade 1-4	
 Continue at the same dose level. 	
 See Sections 5.4.5.5 and 5.4.5.6 and Table 3.
Immune-related AE (irAE)	Grade 1-4	
 Grade 1: continue at the same dose level. Grade 2-4: hold treatment until recovery to Grade ≤ 1 and restart axitinib at the same dose level for Grade 2 and at reduced dose level for Grade 3-4. 	
 See Section 5.4.5.7 and Table 4.
Stevens-Johnson syndrome	Grade 3-4	
 Permanent discontinuation 	
 Permanent discontinuation
Other Non-hematologic Toxicities and Laboratory Abnormalities	Grade 1	
 Continue at the same dose level. 	
 Continue as per schedule
	Grade 2	
 Continue at the same dose level. 	
 Continue as per schedule

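### Axitinib dose changes are classified against the planned dose instead of the preceding level, so some cuts count as escalations and some re-escalations as reductions

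*SAP*

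**What the plan says.** SAP 6.5.3.3, for axitinib: "Dose reduction is defined as a change to a non-zero dose level lower than that planned in the protocol". SAP 6.5.3.4: "Dose escalation is defined as a change to a non-zero dose level upper than that planned in the protocol". For reductions the output is "The number and percentage of patients with at least one dose reduction as well as a breakdown of the number of dose reductions" in the categories 1, 2, 3 and 4 or more, and escalations are tabulated the same way. Patients reduced to 3 or 2 mg and patients escalated to 7 or 10 mg are also summarized.

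Neither definition prints the planned level. It has to be inferred as 5 mg BID. Protocol 5.1 says "All patient will be assigned to starting dose of avelumab 10 mg/kg Q2W plus axitinib 5 mg BID", and SAP 6.5.3 says "Axitinib administered orally BID PO at a dose of 5 mg". The relative dose intensity formula in SAP 6.5.3.2 uses 7 × 2 × 5 mg per week, and the tabulated levels lie on either side of 5 mg.

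Protocol Table 1 lists five levels: 2, 3, 5, 7 and 10 mg BID. Protocol 5.4.5.1 allows escalation to 10 mg BID and reduction, each one level at a time. It adds: "Patients who have undergone dose reduction may also undergo dose re-escalation back to the previous dose level at the discretion of the Investigator". In Protocol Table 2, recurrent hypertension after an earlier reduction leads to "Repeat dose reduction by one lower dose level".

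**The concern.** A count of dose changes needs the direction of each change, and direction is defined only by the level before and the level after. The SAP uses the level after and a fixed reference. That works while a patient moves away from 5 mg BID and fails when the patient moves back towards it. The protocol foresees moves back, both as cuts after escalation and as re-escalations after reduction.

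The primary objective is safety and tolerability, and dose reductions are part of how tolerability is described. Two outputs could be wrong: the breakdown of the number of changes per patient and, on the protocol's usage, the percentage of patients with at least one reduction.

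The exposure table could also disagree with the table of adverse events leading to dose reduction. That table takes its reductions from the action recorded on the AE page (SAP 6.6.1, 6.6.1.2), so an AE-driven cut from 7 to 5 mg BID would appear there while the exposure table shows no reduction. Cuts without an AE record have no such second source.

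**Working it through.** The plan gives no figure of its own on this point, so the check applies the written rule to the dose levels in Protocol Table 1.

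**Inputs.** Levels 2, 3, 5, 7 and 10 mg BID (Protocol Table 1); one level per change (Protocol 5.4.5.1); planned level 5 mg BID (inferred as above); N = 20 (Protocol 9.1).

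**Rule as written.** New level below 5 is a reduction, above 5 is an escalation, equal to 5 is neither.

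**Step 1: the 8 one-level changes.**

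| Change (mg BID) | SAP label | Actual direction | Result |
|---|---|---|---|
| 5 to 7 | escalation | up | correct |
| 7 to 10 | escalation | up | correct |
| 10 to 7 | escalation | down | error |
| 7 to 5 | neither | down | depends on convention |
| 5 to 3 | reduction | down | correct |
| 3 to 2 | reduction | down | correct |
| 2 to 3 | reduction | up | error |
| 3 to 5 | neither | up | acceptable if re-escalations are kept apart |

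Two are clear errors and one depends on convention. On direction alone, 3 to 5 also differs, which makes 4 of 8.

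**Step 2: all paths from 5 mg BID with up to 3 changes.** There are 2, 4 and 6 paths with 1, 2 and 3 changes, 12 in total. Comparison A follows the protocol's usage: any step down is a reduction, a step up to a level not yet received is an escalation, and a step up to a level already received is a separate re-escalation. Comparison B keeps the planned-dose convention but respects direction: a reduction is a step down to below 5, an escalation a step up to above 5. Entries are reductions/escalations.

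| Path | SAP | A | B |
|---|---|---|---|
| 5-3 | 1/0 | 1/0 | 1/0 |
| 5-7 | 0/1 | 0/1 | 0/1 |
| 5-3-2 | 2/0 | 2/0 | 2/0 |
| 5-3-5 | 1/0 | 1/0 | 1/0 |
| 5-7-5 | 0/1 | 1/1 | 0/1 |
| 5-7-10 | 0/2 | 0/2 | 0/2 |
| 5-3-2-3 | 3/0 | 2/0 | 2/0 |
| 5-3-5-3 | 2/0 | 2/0 | 2/0 |
| 5-3-5-7 | 1/1 | 1/1 | 1/1 |
| 5-7-5-3 | 1/1 | 2/1 | 1/1 |
| 5-7-5-7 | 0/2 | 1/1 | 0/2 |
| 5-7-10-7 | 0/3 | 1/2 | 0/2 |

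- Against A, the reduction count is wrong in 5 of 12 and the escalation count in 2 of 12 (5-7-5-7 and 5-7-10-7). Whether a patient had at least one reduction is wrong in 3 of 12 (5-7-5, 5-7-5-7, 5-7-10-7), always as a miss. Whether a patient had at least one escalation is never wrong.
- Against B, 2 of 12 paths have a wrong count (5-3-2-3 and 5-7-10-7), and neither of those yes/no results is wrong.

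These are unweighted counts of possible paths, not expected error rates.

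**Step 3: size in the table.** One patient in 20 is 1/20 = 5 percentage points. If 0, 1, 2 or 3 patients have a path on which the only cuts are missed, the percentage with at least one reduction is understated by 0, 5, 10 or 15 points. The range 0 to 3 is an assumption, since the documents give no frequency.

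**Step 4: a lower-dose group.** SAP 5.2 allows one. If its planned level were read as 3 mg BID, the labels would shift (2 to 3 and 5 to 3 become neither; 7 to 5 and 10 to 7 become escalations), and 4 of the 8 changes would still differ from their direction.

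**The case against.** The best case for the SAP is that a fixed planned-dose reference is coherent and used throughout. Avelumab reductions are measured against the planned dose, axitinib relative dose intensity uses 5 mg BID, and Protocol Table 1 numbers its levels up and down from the starting dose. On that convention, counting 7 to 5 as neither is the rule working as intended, and Comparison B shows no patient wrongly classed as with or without a reduction. The 15-point upper figure therefore rests on the protocol's usage and on an assumed number of patients. This much stands.

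The miscounted moves also need restricted sequences. A cut from 10 to 7 requires two prior escalations, each after 2 consecutive weeks without Grade >2 axitinib-related events, and neither is open to a patient with BP above 150/90 mm Hg or on antihypertensives. A move from 2 to 3 requires two reductions and then at least 28 days free of Grade ≥2 non-hematologic treatment-related toxicity. Cumulative dose and relative dose intensity use actual doses and are unaffected. So is the exclusion of patients with dose changes from the median concentration plots (SAP 6.2.2), because anyone who leaves 5 mg BID gets at least one label. These points limit the importance and are accepted.

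They do not rescue the definitions. A fixed reference can show who was ever below or above the planned dose, but it cannot count changes, and the SAP asks for counts. Even on its own convention, 5-7-10-7 gives 3 escalations where there were 2, and 5-3-2-3 gives 3 reductions where there were 2. Table 2's instruction to go one level down refers to the current level and is not confined to patients at or below 5 mg BID.

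**Conclusion.** The concern holds. Followed as written, SAP 6.5.3.3 and 6.5.3.4 label a 10 to 7 mg BID cut an escalation and a 2 to 3 mg BID re-escalation a reduction, which no convention intends. They also leave a 7 to 5 mg BID cut uncounted, contrary to how the protocol uses the term.

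The certain effect is on the per-patient counts. The effect on the percentage with at least one reduction, 5 points per affected patient, depends on adopting the protocol's usage and on how many such patients occur, possibly none. All of this assumes that the planned level means 5 mg BID. The primary AE and laboratory analyses are untouched. It should be fixed because the stated rule produces wrong table entries and the correction is cheap.

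**What to change.** In SAP 6.5.3.3 and 6.5.3.4:

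- Define an axitinib reduction (escalation) as a change to a non-zero dose level lower (higher) than the immediately preceding non-zero dose level, using the dose modifications recorded in the CRF.
- Report an upward move back to a previously received level after a reduction as a re-escalation in its own row, outside the escalation count.
- Keep the lowest and highest level reached, relative to the starting dose assigned to the patient's cohort, as a separate summary. This retains what the planned-dose comparison is good for and still works if a lower-dose group is added.

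The cost is two or three sentences of SAP text and a small programming change. Protocol 5.4.5 already has axitinib dose modifications reported in the CRF, so no new data collection is assumed. No dosing rule changes.
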